## 12.3 Ancillary mechanistic analyses

The trial incorporates the collection, preparation and storage of biological specimens for mechanistic analyses. The overarching objective of these analyses is to idenfity the key mechanism/s involved in development of liver allograft tolerance, with a particular emphasis in pathways that could be manipulated to intentionally induce transplantation tolerance. The specific aims will be:

- a) to confirm the influence of iron homeostasis in the development of liver transplant tolerance, and how iron homeostasis interacts with clinical and immunological parameters associated with tolerance;
- b) to investigate if immune exhaustion/senescence plays a role in the establishment of transplantation tolerance;
- c) to determine the impact of donor-specific anti-HLA antibodies on the success of IS withdrawal;
- d) to study how the gut microbiome influences the immunogenicity of the transplanted liver and the development of tolerance;
- e) to investigate how these factors might influence changes in the biomarker-status of participants over time.

#### 12.4 Sampling Volumes and biological specimen storage

The biological specimen collection schedule is described in detail in Table 3. Samples will be used to conduct the following studies:

- 1. Quantification of cytokines, micro-RNA, iron and metabolomics parameters in serum.
- 2. Measurement of anti-HLA class I and class II antibodies.

3. Flow cytometry analyses and epigenetic/genomic studies on cryopreserved peripheral blood mononuclear cells (PBMCs). PBMCs will be isolated in a Ficoll gradient and cryopreserved in freezing medium.

4. Gut microbiome sequencing: approximately 1g of fresh stool will be collected at randomisation visit, 18 and 48 months after randomisation. Stool samples will be cryopreserved in RNAlater reagent.

6. Liver tissue gene expression studies: a portion of all protocol and liver tissue samples will be cryoprerved in RNAlater reagent. Gene expression studies will be performed employing microarray and/or digital PCR technology.

7. Liver tissue immunostaining: formalin-fixed and paraffin embedded liver tissue excess clinical material collected as a result of the for-cause or protocol biopsies will be employed to investigate the accumulation of specific lymphocyte subsets using multiplex immunostaining techniques.

## 12.5 Future/Unplanned studies:

As research tests are developed over time, specimens stored during the trial may be used in future assays to address the mechanistic goals of the study. Additionally, samples may be used for assays/ experiments outside the scope of the current study proposal, such as study of differences in the TCR sequence repertoire, proteomics, epigenetics, or other explorations that may emerge during the trial period. Reevaluations or new assays will only be performed on samples of participants who have consented for future research. This will apply as well to consented patients considered non-eligible on the basis of the screening biopsy.

# 13. PROCEDURES FOR RECORDING AND REPORTING ADVERSE EVENTS

Following review by the MHRA, the proposed trial has been considered a test of efficacy of the IS, and therefore a Clinical Trial of an Investigational Medicinal Product (CTIMP) according to the EU Clinical Trial Directive 2001/20/EC. For the purposes of this trial these drugs are defined as IMPs (Investigational Medicinal Products) but they will not require special labelling/accountability/storage etc.

For assessment of safety, we will follow the definitions given by the Medicines for Human Use Regulations 2004 and Amended Regulations 2006:

- Adverse Event (AE): Any untoward medical occurrence in a subject to whom a medicinal product has been administered including those that are not necessarily caused by or related to that product.
- Adverse Reaction (AR): Any untoward and unintended response in a subject to an investigational medicinal product, which is related to any dose administered to that subject.
- Unexpected Adverse Reaction (UAR): An adverse reaction the nature and severity of which is not consistent with the information about the medicinal product in question set out in the SmPCs for the IS medications employed by the participants enrolled in the study.
- Serious adverse Event (SAE), Serious Adverse Reaction (SAR) or Unexpected Serious Adverse Reaction (USAR): Any adverse event, adverse reaction or unexpected

adverse reaction, respectively, that results in death; is life-threatening; required hospitalisation or prolongation of existing hospitalisation; results in persistent or significant disability or incapacity; consists of a congenital anomaly or birth defect. Although not a serious adverse event, any unplanned pregnancy will also be reported via the SAE reporting system.

# 13.1 Reporting Responsibilities in the United Kingdom, Germany, Spain, Italy and Belgium

The delivery of the sponsor's responsibility for Pharmacovigilance (as defined in Regulation 5 of the Medicines for Human Use Regulations 2004) has been delegated to King's Health Partners Clinical Trials Office (KHP-CTO). The Chief Investigator (CI) will immediately (and no later than 24hrs) report to the KHP-CTO all SAEs, SARs and SUSARs in accordance with the current Pharmacovigilance Policy. Important Medical Events that may not be immediately life-threatening or result in death or hospitalisation but may jeopardise the patient or may require intervention to prevent one of the other outcomes listed in the SAE definition should also be considered serious and reported using the SAE form. The KHP-CTO will report SUSARs to the regulatory authorities (MHRA). The CI will report to the relevant ethics committee. Reporting timelines are as follows:

- SUSARs that are fatal or life threatening must be reported within 7 days after the sponsor is first aware of the reaction. Any additional relevant information must be reported within a further 8 days.
- SUSARs that are not fatal or life threatening must be reported within 15 days of the sponsor first becoming aware of the reaction.

The CI and KHP-CTO (on behalf of the sponsor), will submit annually to the MHRA and REC, a Development Safety Update Report (DSUR). The CI will submit annually to the main REC an Annual Progress Report. For the purposes of this study, graft rejection does not constitute an SAE, and will be recorded in a dedicated section in the case report form (CRF). Pregnancy is not considered to be an AE or SAE. However, the trial centre should report any pregnancy in a trial patient to the Sponsor within 24 hours of becoming aware of the pregnancy, using the dedicated paper form supplied by the Sponsor. A pregnancy should be carefully monitored and the Investigator should track the progress of the mother and the foetus as if the pregnancy were an SAE, providing detailed information to the Sponsor as it becomes available. During gestation, any occurrences that result in a SAE should be reported on the paper SAE Form as per the SAE reporting procedure. The Investigator must follow all patient pregnancies to term and report the outcome to the Sponsor. When the outcome of a pregnancy falls under the criteria for an SAE (e.g. spontaneous or induced abortion, stillbirth, death of newborn, congenital anomaly, birth defect) the Investigator should

respond by submitting an SAE report. The Sponsor will report pregnancy outcomes to the regulatory authorities.

#### 13.2 Reporting Responsibilities in Ireland

The delivery of the sponsor's responsibility for Pharmacovigilance (as defined in Regulation 5 of the Medicines for Human Use Regulations 2004) has been delegated to King's Health Partners Clinical Trials Office (KHP-CTO). The Chief Investigator (CI) will immediately (and no later than 24hrs) report to the KHP-CTO all SAEs and SARs in accordance with the current Pharmacovigilance Policy. Important Medical Events that may not be immediately life-threatening or result in death or hospitalisation but may jeopardise the patient or may require intervention to prevent one of the other outcomes listed in the SAE definition should also be considered serious and reported using the SAE form. SUSARs occurring in Ireland will be reported by the HPRA to the Eudravigilance (EVCTM) on the Sponsor's behalf. The HPRA will require SUSAR reports in an expedited fashion to ensure the HPRA and reporting timelines are as follows:

- SUSARs that are fatal or life threatening must be reported within 3 days after the sponsor is first aware of the reaction. Any additional relevant information must be reported within a further 8 days.
- SUSARs that are not fatal or life threatening must be reported within 9 days of the sponsor first becoming aware of the reaction.

The CI and KHP-CTO (on behalf of the sponsor), will submit annually to the HPRA, a Development Safety Update Report (DSUR). For the purposes of this study, graft rejection does not constitute an SAE, and will be recorded in a dedicated section in the case report form (CRF). Pregnancy is not considered to be an AE or SAE. However, the trial centre should report any pregnancy in a trial patient to the Sponsor within 24 hours of becoming aware of the pregnancy, using the dedicated paper form supplied by the Sponsor. A pregnancy should be carefully monitored and the Investigator should track the progress of the mother and the foetus as if the pregnancy were an SAE, providing detailed information to the Sponsor as it becomes available. During gestation, any occurrences that result in a SAE should be reported on the paper SAE Form as per the SAE reporting procedure. The Investigator must follow all patient pregnancies to term and report the outcome to the Sponsor. When the outcome of a pregnancy falls under the criteria for an SAE (e.g. spontaneous or induced abortion, stillbirth, death of newborn, congenital anomaly, birth defect) the Investigator should respond by submitting an SAE report. The Sponsor will report pregnancy outcomes to the regulatory authorities.

## 14. STOPPING CRITERIA

The Sponsor and CI reserve the right to stop the trial at any time, for any justifiable reason. These include, among others:

- 1) request from the Data Monitoring & Ethics Committee (DMEC) or a regulatory authority;
- 2) failure to meet patient recruitment targets;
- 3) serious and/or persistent non-compliance with the trial protocol;
- 4) non-compliance with ethical standards, regulatory requirements or GCP;
- 5) when the Sponsor/chief investigator is aware of important new information that adversely affects the conduct of the study;
- 6) Findings uncovered during monitoring visits, trial audits or inspections that compromise the suitability of the site to act as a trial centre.

In the event of premature discontinuation, the Sponsor will promptly notify the responsible regulatory authorities, and provide a detailed written explanation of the reasons for early termination. The affected trial participants will also be informed promptly and appropriate follow-up will be arranged. The CI will also inform the REC.

During the course of the study any of the following will pause the study and trigger a review by the DMEC: 1) death or graft loss in any study subject; and 2) composite incidence of severe acute rejection, steroid resistant acute rejection, or chronic rejection >5% (this composite end point will be monitored on a regular basis by the Study Statistician, who will estimate its incidence and exact one-tailed 90% CI and check whether the lower bound of the CI is above the pre-set threshold of 5%.).

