### 5.4 Trial Design

This is a prospective, multi-centre, phase IV, biomarker-strategy design trial with a randomised control group in which adult liver transplant recipients will undergo IS withdrawal. Enrolled participants will be randomised 1:1 to either: 1) Non-Biomarker-based IS weaning (Weaning-All; Arm A); or 2) Biomarker-based IS weaning (Arm B). In participants allocated to Arm A IS will be withdrawn regardless of the result of the biomarker test. Among participants allocated to Arm B, only those found to be biomarker-positive (Arm B+, i.e. potentially tolerant) will be offered IS withdrawal, while biomarker-negative participants (Arm B-, i.e. potentially non-tolerant) will remain on their

baseline maintenance IS. This will allow us to demonstrate that the biomarker is a useful test to personalise IS by offering drug withdrawal only to those participants who are likely to complete the process successfully, avoiding unnecessary rejections among those who have not developed tolerance. Comparing the outcome of IS withdrawal between arms A and B+ will provide direct evidence of the clinical usefulness of the test as a function of its predictive accuracy. We have established that for the biomarker to drive safe IS withdrawal its Positive Predictive Value  $(PPV = \frac{Number Actually Tolerant}{Number Biomarker+})$  should be no less than 0.80, and its sensitivity at least 070. To account for centre effects, we will use stratified randomization. Furthermore, to avoid biases, participants undergoing drug withdrawal and their physicians will be blinded to the biomarker results. Participants randomized to Arm B- will know their biomarker status, and will be maintained in the study until they complete 48 months of follow-up post randomisation. They will contribute to secondary clinical outcomes and to the evaluation of the stability of the tolerance signature.

Cost and quality of life (HrQOL) assessments will be conducted alongside the trial to estimate the health-economic implications of the 2 different strategies. Furthermore, sequential biological specimens will be collected to conduct ancillary mechanistic studies. Recruitment will take place in 14 European liver transplant units (King's College Hospital, Royal Free London, Newcastle, Birmingham, Leeds, Edinburgh, Cambridge, Leuven, Hannover, Berlin, Barcelona, Dublin, Cliniques Universitaires Saint-Luc and Palermo-ISMETT).

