#### 18.2 Trial Steering and Data Monitorning and Ethics Committees

A Trial Steering Committee (TSC) will be convened. The membership will be decided by the CI in partnership the sponsor. The chair will be a senior transplantation physician or surgeon from the UK who is unconnected to the study. Members will include the CI, two other PIs from the trial, 2 representatives of the liver transplant patient organisation LISTEN, as per INVOLVE recommendations, and 2 other senior independent transplant physician/surgeons (at least one of them from overseas). In addition, a Data Monitoring and Ethics Committee (DMEC) will be established comprising a senior UK-based transplant physician/surgeon as chair, a liver transplant physician/surgeon from overseas and a biostatistician. All the members will be independent of the trial. The DMEC will meet every 3 months throughout the duration of the trial. In addition, the DMEC will meet in the occurrance of any of the following (or at any time required by the CI, the sponsor or the EME board): 1) death or graft loss in any study subject; and 2) composite incidence of severe acute rejection, steroid resistant acute rejection, or chronic rejection >5% (this composite end point will be every 3 months by the Study Statistician, who will estimate its incidence and exact one-tailed 90% CI and compare it to pre-defined thresholds). The TSC will meet on a six monthly basis throughout the period of the trial, and at other times deemed necessary by the CI, the sponsor or by the EME board. A Trial Management group will be established, to include the CI, statisticians and the project manager. This will meet monthly to manage the set up and ongoing conduct of the trial. In addition, there will be regular (6 monthly) meetings of the PIs, alternating

face-to face with videoconferences. The trial has been reviewed by the Institute of Liver Studies R&D Governance Board at King's College Hospital, which provides research governance oversight for all liver trials instituted at King's College Hospital, as well as by representatives from the liver transplant patient association LISTEN.

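### The severe-rejection trigger in Sections 14 and 18.2 has no stated denominator or biomarker split; either pooled reading detects an excess in weaned biomarker-negatives poorly.

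*Protocol*

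**What the plan says.** Section 14 lists two events that pause the study and bring a DMEC review. The first is "death or graft loss in any study subject". The second is "composite incidence of severe acute rejection, steroid resistant acute rejection, or chronic rejection >5"%, for which the study statistician is to compute an "exact one-tailed 90% CI and check whether the lower bound of the CI is above the pre-set threshold of 5"%.

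Section 18.2 gives the same two events as reasons for the DMEC to meet. For the second, the statistician is the one "who will estimate its incidence and exact one-tailed 90% CI and compare it to pre-defined thresholds", every 3 months. This section mentions no lower bound, gives no threshold values beyond the headline 5%, and does not mention a pause.

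Neither section names the participants over whom the incidence is taken, and neither asks for it by arm or biomarker status. Section 5.4 sets the exposure: "In participants allocated to Arm A IS will be withdrawn regardless of the result of the biomarker test", while biomarker-negative participants in Arm B stay on maintenance treatment. Weaned biomarker-negatives therefore exist only in Arm A.

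**The concern.** A rule that can pause a trial has to identify its numerator and denominator without interpretation. Here the denominator could be all participants or only those being weaned, and the choice changes how many events are needed.

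It matters more in this design because risk is uneven by construction. About a quarter of participants (B-) are not weaned under the protocol and mainly add to a study-wide denominator. Another quarter (A-) are weaned although the test classes them as probably not tolerant. If severe rejection concentrates in A-, a single pooled proportion averages that quarter with three quarters at lower or no weaning exposure. The rule could then stay silent while the rate in A- is several times 5%.

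The difference in wording adds to this. Section 14 fixes a lower-bound test and a pause. Section 18.2 leaves the comparison open and provides for a meeting. A statistician working from one section need not apply the rule in the other.

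**Working it through.** **Group sizes.** Section 15 gives 0.50 against 0.80 success, 90% power, 5% type I error, a 2:1 ratio of A to B+, and 50% biomarker-positive. With a two-sided test and unpooled variances, n(A) = (1.960 + 1.282)² × (0.50×0.50 + 0.80×0.20/0.5) / 0.30² = 66.5, so 67 in A and 33 in B+, total 100. Adding about 34 in B- gives 134, and 134 × 1.10 = 147.4, so 148. The plan's 100, 134 and 148 are reproduced. At 148, 1:1 allocation and 50% positive give 148 × 0.5 × 0.5 = 37 in each of A+, A-, B+ and B-. The weaned number 37 × 3 = 111, if all in A and B+ start withdrawal.

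**Events needed.** The plan states no event boundary for the rule, so it is derived here. The exact one-sided 90% lower bound for x events in n is the 10th percentile of Beta(x, n − x + 1). The rule fires at the smallest x whose bound exceeds 5%.

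| Denominator | One event fewer: bound | Fires at | Observed rate | Bound |
|---|---|---|---|---|
| All 148 | 11: 4.79% | 12 | 8.1% | 5.35% |
| Weaned, 111 | 9: 4.95% | 10 | 9.0% | 5.68% |
| A-, 37 | 4: 4.80% | 5 | 13.5% | 6.72% |

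If Section 18.2's headline were read as a point estimate above 5%, 8 of 148 would be enough, not 12.

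**Chance of triggering.** Exact binomial probabilities were combined over A- (37), biomarker-positive weaners (74) and B- (37). All rates are assumptions, because the plan gives none.

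| A- | Positive weaners | B- | All 148 | Weaned | A- alone |
|---|---|---|---|---|---|
| 10% | 10% | 0% | 43% | 68% | 31% |
| 10% | 0% | 0% | <1% | <1% | 31% |
| 10% | 2% | 1% | 1% | 3% | 31% |
| 15% | 0% | 0% | 1% | 4% | 67% |
| 15% | 2% | 1% | 6% | 16% | 67% |
| 20% | 0% | 0% | 5% | 19% | 89% |
| 20% | 2% | 1% | 20% | 39% | 89% |
| 20% | 5% | 0% | 43% | 69% | 89% |
| 30% | 0% | 0% | 43% | 71% | 99% |
| 30% | 2% | 1% | 67% | 85% | 99% |

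The 20%/0%/0% row shows the mechanism: 37 × 0.20 = 7.4 expected events, and 7.4/148 = 5.0%. The study-wide rate sits at the threshold although A- runs at four times it.

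**False triggers at a true 5% in everyone weaned.** With B- at 0% the chance is 1.0% over all 148 and 5.2% over the weaned. With B- also at 5% it is 6.8% and 5.2%.

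**Repeated looks.** Simulating 3-monthly looks over an assumed 18-month uniform accrual moves the trigger chances above by about one percentage point.

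**The case against.** The strongest reply is that the protocol never says the incidence runs over the whole study. A reader might infer this because the trigger is listed next to "death or graft loss in any study subject", but that phrase belongs to the separate death and graft-loss trigger. A weaned-only denominator fits the text equally well. This stands: the denominator is undefined, not fixed study-wide. It does not remove the point, because the weaned-only reading also gives only 19-39% in the 20% scenarios with 0-2% in positive weaners.

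A reader might also infer that A- has no other protection. The protocol does not support that. One death or graft loss pauses the study. Section 18.2 says "The DMEC will meet every 3 months throughout the duration of the trial", the DMEC can request a stop, liver tests are 3-weekly during weaning, and rejection is handled patient by patient. These are real safeguards. None of them requires the DMEC to see the composite by biomarker status, though. Sections 13.1 and 13.2 exclude graft rejection from SAEs, and the interim analyses in Section 16.3 concern only PPV and sensitivity.

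It would go too far to carry Section 15's weaning-failure rates (implying about 80% failure in A- and 20% in positives) over to severe rejection. Failure includes not starting, not completing, and histological change, and Section 4.2 expects severe episodes to be extremely unlikely. The documents give no severe-event rate for any stratum and call no subgroup rate unacceptable.

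Finally, Section 18.2's wording is compatible with Section 14's: its thresholds could be the 5% bound, and a meeting can accompany a pause. That is fair, but Section 18.2 does not say so.

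**Conclusion.** The point holds as a defect of definition with a measurable effect on a safety rule. Sections 14 and 18.2 leave the denominator open, do not separate biomarker strata, and do not describe the comparison and its consequence in the same terms.

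The choice of denominator alone moves the trigger chance from 43% to 68% at a uniform 10% in the weaned with none in B-. For an excess confined to A-, both pooled readings are weak at 10-20% when rates elsewhere are low.

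It does not follow that the rule rarely fires. At 30% in A- the study-wide chance is 43-67%, and at 20% in A- with 5% in positive weaners and 0% in B- it is 43%. The figures rest on 37 per stratum, everyone in A and B+ starting withdrawal, and assumed event rates. If Arm A held 30 or 44 biomarker-negatives, the study-wide chance at 20% in A- with no events elsewhere would be 1% or 15% instead of 5%. This is a cheap improvement worth making, not evidence that the trial is unsafe.

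**What to change.** - In Sections 14 and 18.2, define the incidence over participants who have started IS withdrawal (Arms A and B+). Leave the 5% threshold and the exact one-tailed 90% bound unchanged.
- Reconcile the two sections so that both state the same comparison and the same consequence. Which consequence applies is for the sponsor and the DMEC to settle.
- In the closed 3-monthly DMEC report, also show the incidence and bound for weaned biomarker-negatives (A-). Any action on that line is left to the DMEC; it is not a new binding trigger.

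**Cost.** This takes a sentence or two in each section and one extra closed table from data already collected. The table shows biomarker status, so it must stay away from blinded participants and physicians. Section 18.2 places statisticians in the Trial Management Group with the Chief Investigator, so access needs care. If B- has almost no events, the false-trigger chance at a true 5% in the weaned rises from about 1% to about 5%. The A- line would itself cross by chance about 4% of the time at a true 5% (3.6% at a single look).
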